Recently, research criteria and neurobiological models are set to prioritize factors to study and use them in a personalized precision psychiatry (RDoc-criteria of the National Institute of Mental Health, NIMH <https://www.nimh.nih.gov/research-priorities/rdoc/>; Heuvel et al., 2016, Williams 2016). These models are close to the above-mentioned psychological candidate predictors of treatment outcome: 1) cognitive factors or ‘cognitive’ brain networks, 2) affective factors related to the ‘limbic’ brain networks, and 3) relational factors related to the ‘positive affect’ and social processing brain networks (see figure 1 below). Using these models will help to build a more dimensional instead of categorical psychiatric model that will be better applicable to treatment choice (Williams 2016).

Preliminary evidence exists on neurohormonal and associated (epi)genetic predictors of treatment outcome. A serotonin transporter gene promoter-region polymorphism (the LL 5HTTLPR genotype) was associated with greater responsiveness of PTSD to pharmacotherapy, while the S allele was associated with treatment non-response (Schmidt et al., 2013). Lower brain derived neurotrophic factor (BDNF) levels predicted a greater response to pharmacotherapy in PTSD (Schmidt et al., 2013). It is not clear yet if these factors might predict psychotherapy outcome as well. Cortisol levels and FKBP-5 predicted PTSD susceptibility and might be useful as a treatment outcome marker too (Schmidt et al., 2013, Galatzer-Levy et al., 2017). The same holds for oxytocin and the oxytocin receptor (OXTR) gene (Bandelow et al., 2016; 2017)

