score of ≥ 2 in each of the three CPTSD symptoms clusters, plus functional impairment associated with these symptoms. A patient can only receive a PTSD or a CPTSD diagnosis, not both. The ITQ has demonstrated adequate internal reliability and validity (Cloitre et al., 2018; Hyland et al., 2017).

5.1.3 Biological predictors (see table 2):

- Biological parameters
 - Body measures: Weight, height, blood pressure
 - HPA axis (cortisol): Hair sample
 - Biomarkers: Fasting blood sample (BDNF, FKBP-5) & Full blood
- MRI session in subsample (60 min)
 - 3 Tesla-MRI (GE, VUmc): functional MRI with a face recognition , Structural MRI, Resting state MRI, DTI. In between scans a visual analogue scale (VAS) will be applied to assess distress during the scan session.

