⊗ Timing of the T2 measurement will be directly after trauma treatment, around 6 months

#The SCID-5-P at T0 is part of the regular intake procedure at the Sinai Centre

Table 2: Overview of add-on cognitive task, biological measurements, including MRI

MEASUREMENTS		DURATION	To	T1	T2	T3	T4	FU
in months			0	3	6 [⊗]	9*	12	18
COGNITIVE TASKS AT DAY 2		10 min						
Working memory	N-back	10	X*					
Interference	Stop/Signal task	15	X*					
PHYSICAL EXAMINATION AT DAY 2		30 min						
Body measures	Weight, height	10	X					
Blood pressure	Systolic and diastolic	5	X					
HPA axis (Hair)	Hair sample (cortisol)	5	X		X			
Biomarkers	Fasting blood sample (5HTTLPR, BDNF, FKBP5, oxytocin/OXTR) & Full blood	10	X		X			
MRI SESSION IN SUBSAMPLE WITHIN 2 WEEKS		60 min						

Functional MRI	Face recognition task	15	X		X			
Structural MRI		7	X		X			
Resting state MRI		10	X		X			
DTI		10	X		X			

DTI = Diffusion Tensor Imaging, MRI = Magnetic Resonance Imaging.

[&] Timing of the T2 measurement will be directly after trauma treatment, around 6 months

* Timing of the T3 measurement will be 3 months after T2, around 9 months

Table 3: Overview of duration of measurements (in minutes)

	To	T1	T2	T3	T4	Follow-up
Interviews	45	-	45	-	195	-
Questionnaires	91	15	88	15	88	27
n-back	10	-	-	-	-	-
TOTAL	141 (ca. 2.5 hrs)	15	128 (ca. 2 hrs)	15	278 (ca. 4,5 hrs)	27
Blood/hair	30	-	30	-	-	-
MRI	90	-	90	-	-	-
TOTAL for subgroup with MRI/blood/hair	261 (ca. 4 hrs)	15	218 (ca. 3,5 hrs)	15	278 (ca. 4,5 hrs)	27

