Blood samples will be collected in 3 x 6ml tubes and the frozen samples will be stored at -80°C for intended future assaying of inflammatory markers (see Coelho et al., 2014), neuropeptides (such as oxytocin, 5HT), and epigenetics (such as FKBP5-methylation, OXTR- & 5HTTLPRgenes). The tubes will be stored without personal data linked to it, and they will only be marked with a subject number as described in section 9.1. below. Cortisol level (HPA-indicator) will be assessed in hair. This sample can be collected non-invasively by cutting a 1-cm distal to the scalp (1 month's exposure) sample of hair (Russell et al., 2012). All samples will be stored for 15 years (according to Archiefwet 1995).

In a subgroup: MRI session

Exclusion criteria for MRI research will be checked (metal implants, pregnancy, somatic disorders interfering with brain functioning, other (psycho-)pharmaca than at-least-3-months stabile dose SSRI or low-dose benzodiazepines, claustrophobia). A separate visit for MR scanning will be planned within 2 weeks of To, before the start of treatment, without causing a delay in treatment start. MRI sessions take at maximum 60 minutes (30-min functional MRI with a face recognition, and a suppression vs. reappraisal task, 5-min structural MRI, 8-min resting state MRI; and 8-min DTI) plus 30 min preparation. Next to patients, 40 healthy control persons, matched for age, gender, and education, will be asked to participate in one MRI session (no repeat MRI). These healthy control persons will be recruited via advertisements in local papers.

T1, T3 and FU

Patients do not have to come to the study center for T1, T3 and FU and can fill in the questionnaires via a login code at home if they have access to the internet (see Table 1.). Child trauma and life events questionnaires are only done at baseline (CTQ, LEC-5). Total duration of these measurements (T1, T3 and FU) will be between 15 and 30 minutes (see Table 3).

T2 visit

From all participants whose blood and hair was collected at baseline, blood and hair will be collected at T2 as well (duration 30 minutes). All participants who participated in the fMRI study at baseline will have their second MRI at T2. (duration 90 minutes). At T2, the CAPS-5 will also be conducted and participants will fill out the same questionnaires as at T0, except for the CTQ and LEC-5. Total duration of these measurements of will be ca. 2 hours (see Table 3).

Extra contact moment

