7.1 Primary study parameters

For population description, the CAPS-5, M.I.N.I.-plus, SCID-5-PD, will be used in addition to the CTQ, LEC-5, DERS, ITQ, PAI-BOR, STAS, PSQI, DES-II, WAV, RSQ, CPI, BDI, AUDIT, WHODAS, EQ5D-5L, and Tic-P will be used (see Table 1). The subgroup of patients that underwent MRI will be compared to the rest of the group to test for pretreatment differences in PTSD severity and type/severity of PD.

The primary analysis in the RCTs will be improvement of PTSD symptoms at 3 time points. This primary analysis will include trauma symptom scores at T₀, T₂ and T₄ (CAPS-5, severity score) in a repeated measurements model, a linear mixed model for repeated measurements including at least time points, treatment group, the interaction between time point and treatment, sex, age and severity as fixed factors, baseline score as covariate and subject as random intercept factor. An cAR(1) structure will be used to model the residual covariance matrix. Responders will be defined as participants with a posttest score at least 1 SD below the pretest score (based on Jacobsen and Truax, 1991).

Secondary analyses will examine whether hormonal and epigenetic factors (5-HTTLPR, BDNF, cortisol/FKBP5-methylation, oxytocin/OXTR) mediate the treatment effects. Mediation analyses will include levels of the aforementioned variables on T₀ and T₂ to estimate the direct and indirect paths of casual treatment on the primary and secondary study parameters, through the proposed mediators.

For individual prediction analyses, machine learning techniques (in R: supervised and unsupervised techniques, e.g. the random forest model method) will be applied to separate treatment responders from non-responders based on clinical and neurobiological candidate predictors and in order to define the predictors

contributing most to classification accuracy, calculating sensitivity, specificity, and positive and negative likelihood ratios from the prediction model (Ball et al., 2014).

Candidate predictors that will be used are:

- Psychological factors: Cognitive factors (educational level/IQ, working memory, emotion regulation), Affective factors (hyperarousal: anger, sleep; hyperarousal: dissociation), and Relational factors (therapeutic alliance, attachment, social support);

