- Neurobiological factors: Neural factors (smaller ACC and hippocampus volume, increased right amygdala and ventral ACC activity and de/increased dorsal ACC activity), and Hormonal/ epigenetic factors (5-HTTLPR, BDNF, cortisol/FKBP5-methylation, oxytocin/OXTR).

Questions that will be answered with machine learning in this study are:

1. Does brain activity predict treatment outcome for PTSD and PD (all treatment conditions together; N = 80)
2. Does brain activity predict treatment outcome for PTSD (EMDR and ImRs; N = 40)
3. Does brain activity predict treatment outcome for integrated PD/PTSD treatment (EMDR + DBT and ImRs + SFT, N = 40)
4. Data from the MRI at T2 can be used to predict relapse after treatment for all treatments together (N = 80 if all patients return for a second MRI) or for trauma treatment and integrated treatment separately (N = 40 for both).

fMRI data will be analysed with Statistical Parametric Mapping (SPM) software or FMRIB Software Library (FSL) to map connectivity in the brain. Standard group comparisons will be used to analyse structural and task-related (face recognition) fMRI. First, ANOVA analyses will be performed with patients vs. controls for baseline comparison. Second, full factorial analyses will be conducted in patients-only, with time (baseline vs. end of treatment) and condition (type of treatment) as factors to analyse the effect of treatment on (task-related) brain structure, connectivity and activity. Independent component analysis (ICA; FSL MELODIC) and dual regression analyses will be used to study changes in functional connectivity of brain networks (with a focus on the salience

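### Therapeutic alliance has no T0 measure in Table 1 yet is a candidate predictor for treatment indication; secondarily, no changeable quantity is defined for the 5-HTTLPR and OXTR mediators

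*Combined protocol and SAP*

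**What the plan says.** **Prediction.** Section 2 places objective B among the primary objectives: individual prediction of PTSD treatment outcome by machine learning, with better treatment indication as its purpose. Therapeutic alliance is named there as a relational factor, and section 7.1 repeats it in the list of candidate predictors to be used. Section 7.1 gives no measurement time for any psychological predictor. Table 1 schedules the alliance questionnaire (WAV) and leaves its T0 cell empty. Two other places read differently. The Summary counts relational factors among the candidate predictors taken at baseline. The T2 visit paragraph of section 5.3 says that the T2 questionnaires are those of T0 apart from the CTQ and LEC-5.

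**Mediation.** Section 7.1 says: "Secondary analyses will examine whether hormonal and epigenetic factors (5-HTTLPR, BDNF, cortisol/FKBP5-methylation, oxytocin/OXTR) mediate the treatment effects". It continues: "Mediation analyses will include levels of the aforementioned variables", at T0 and T2. On what the two genetic items are:

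- Section 1, Part B, introduces 5-HTTLPR with "A serotonin transporter gene promoter-region polymorphism (the LL 5HTTLPR genotype" and says of OXTR: "The same holds for oxytocin and the oxytocin receptor (OXTR) gene".
- The blood-sample text of section 5.3 lists "epigenetics (such as FKBP5-methylation, OXTR- & 5HTTLPRgenes".
- Section 5.1.3 lists only "Fasting blood sample (BDNF, FKBP-5) & Full blood".
- Table 2 lists "Fasting blood sample (5HTTLPR, BDNF, FKBP5, oxytocin/OXTR) & Full blood", marked at T0 and T2.
- The predictor list in section 7.1 has the same items: "Hormonal/ epigenetic factors (5-HTTLPR, BDNF, cortisol/FKBP5-methylation, oxytocin/OXTR".

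**The concern.** A model meant to help choose a treatment can use only what is known before the choice. Alliance is formed with a therapist during treatment. If it is first recorded after allocation, a classifier that includes it can look accurate in the trial data and still have no such input at intake. Its sensitivity, specificity and likelihood ratios would then describe a situation other than the one objective B is about.

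The mediation question is separate. A mediator has to be something treatment can move. An inherited genotype is not, so a plan to take its value twice and estimate a path from treatment through it would say nothing about mechanism. What is at stake is the prediction objective and a secondary mechanistic analysis.

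**Working it through.** **1. When is alliance measured?** The WAV row of Table 1:

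| | T0 | T1 | T2 | T3 | T4 | FU |
|---|---|---|---|---|---|---|
| Month | 0 | 3 | about 6 | about 9 | 12 | 18 |
| WAV | empty | differently printed mark | X | X | empty | empty |

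The T1 mark is not the usual X. A similar odd mark appears for the NSSI at T3 and the PAI-BOR at follow-up. It may be a real entry, a deletion or a text-conversion artefact. Taking both readings:

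- T1 mark real: first alliance score at about 3 months, when trauma treatment (3 to 6 months in the Summary) is under way or just ending.
- T1 mark not real: first score at T2, which section 3 places after trauma treatment has finished.

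At T3 the PTSD-only arms are, by the Summary, in the planned pause, while the integrated arms are scheduled to run to 12 months. The score therefore does not have the same meaning in the two arms. On either reading of T1, nothing is available at T0.

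**2. Is alliance an exception?** Section 7.1 names nine psychological predictors. Compared with the T0 column of Tables 1 and 2:

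- Measured at T0: education (assumed to come from the demographic questionnaire), working memory (N-back), emotion regulation (DERS), anger (STAS), sleep (PSQI), dissociation (DES-II), attachment (RSQ), social support (CPI). Count: 8.
- Not measured at T0: therapeutic alliance (WAV). Count: 1.

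8 + 1 = 9, so alliance is the only one without a T0 measure.

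**3. Size of the effect on accuracy.** This cannot be computed. The documents give no alliance-outcome correlation and no target accuracy.

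**4. Mediation, if genotype is what is assayed.** Let A be treatment, M0 and M2 the mediator at T0 and T2, and Y the outcome. The assumption is that a genotype does not change within a person, so M2 = M0 for every patient.

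- Change: M2 − M0 = 0 for all patients.
- Mediator model M2 = i + a·A + c·M0: the exact solution is i = 0, a = 0, c = 1.
- Indirect effect: a × b = 0 × b = 0, whatever b is.
- Outcome model with intercept, A, M0 and M2: two of the four columns are identical, so the rank is 3 of 4. Only the sum of the M0 and M2 coefficients can be estimated.
- If M0 is left out, a estimates only the chance imbalance in genotype between the arms, whose expectation under randomisation is zero.

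None of this depends on sample size or allele frequency.

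**5. How many mediators are concerned?** The list has four comma-separated entries, two of them slash pairs. Split out, these are 5-HTTLPR, BDNF, cortisol, FKBP5 methylation, oxytocin and OXTR, six names, of which two (5-HTTLPR and OXTR) are called genes. The plan does not say whether OXTR would have a model of its own or be taken together with oxytocin.

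**The case against.** **Baseline WAV.** Two places in the text imply one, and only a single table row does not. That stands as far as it goes: a reader might infer that Table 1 governs, but the documents do not say so. They contradict each other and have to be reconciled. Even if a T0 WAV exists, T0 precedes the start of treatment, so the plan would need to say which alliance is being rated.

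**Post-baseline predictors are part of the plan.** The fourth machine-learning question in section 7.1 deliberately uses T2 MRI to predict relapse, all four enumerated questions concern brain imaging, and section 1 calls the machine-learning work exploratory. All true. A later predictor is not wrong in itself. Alliance is also a proper variable for questions A1.4 and A2.4 in section 5.3, which ask what predicts outcome and not what to choose. The objection does not cover a model whose stated purpose is treatment indication.

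**Timing.** A reader might infer that alliance is first measured only after trauma treatment. The T1 mark prevents that conclusion. The point rests on the empty T0 cell alone.

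**Epigenetic label.** A reader might infer that the documents treat 5-HTTLPR purely as a genotype and that the mediation analysis is therefore wrong as planned. They do not support this. 5-HTTLPR and OXTR are repeatedly classed under hormonal or epigenetic factors, the genotype wording in section 1 summarises earlier pharmacotherapy findings, and section 5.3 stores samples for future assays with examples only. Methylation may have been meant. It is, however, attached by name only to FKBP5, and no changeable quantity is defined for the other two.

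**Conclusion.** The main point holds. On the Table 1 schedule, alliance cannot inform the initial treatment choice, and an indication model that includes it would report an accuracy not available at that moment. This concerns 1 of 9 named psychological predictors; the effect on accuracy is unknown. It assumes that Table 1 is right about T0, which two other places put in doubt.

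The secondary point holds conditionally. If 5-HTTLPR and OXTR are genotyped, their indirect effects are zero by construction, which affects 2 of 6 named factors. If methylation is meant, mediation can be estimated, but the plan does not yet define the variable.

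The primary CAPS-5 comparison is untouched in either case. Both matters should be settled in writing before analysis.

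**What to change.** **Section 7.1, prediction.** State that the model intended for treatment indication uses T0 variables only and excludes alliance. Report alliance in a separate analysis under A1.4 and A2.4, labelled as a during- or post-treatment predictor that cannot be used to choose treatment. Keep the T2-MRI relapse question as its own model.

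**WAV schedule.** Reconcile Table 1, including the T1 mark, with the Summary and the T2 visit text of section 5.3.

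**Section 7.1, mediation.** Limit the mediators to quantities that can change between T0 and T2: BDNF, hair cortisol, FKBP5 methylation and oxytocin. Keep 5-HTTLPR and OXTR genotype as baseline predictors, where section 7.1 already lists them. If methylation of these genes is intended, name it in section 7.1 and in Table 2.

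**Cost.** Wording changes only and no new data. The indication model loses one candidate predictor, and its apparent accuracy may be lower.

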Use of co-intervention: Patients may continue taking medication for PTSD throughout the study. Patients who started with new medication for PTSD within 1 month prior to the initial screening will be excluded from participation. No other psychological or new pharmacological therapy is allowed during treatment. Medication use is monitored during the study.

Escape medication/treatment: Participants might start taking medication or another form of treatment/therapy in case of acute crisis during the study. The use of these medications or crisis intervention during the study as co-intervention will not lead to exclusion from the study, but will be monitored, documented, and reported.

Further treatment: After completion of the EMDR or ImRs a first follow-up assessment will be completed and the therapist will see the patient for an evaluation. If more treatment is acutely needed, a clinical evaluation is done and the indication staff will decide what treatment to offer to the patient. The kind, intensity and frequency of this further treatment will be monitored, documented and reported. All patients in Zorgpad 1 are allowed to start SFT or DBT after T4 (i.e. 6 months after completing Zorgpad 1).

18

Figure 2. Flow chart for two connected randomized controlled trials (RCTs) for patients with PTSD and borderline personality disorders (BPD) resp. with PTSD and cluster C personality disorders (CPD)

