All patients coming to the Sinai Center are asked to fill in the ROM questionnaires before the intake as part of standard care (OQ-45, LEC-5/PCL-5, SCID-5-PD screener, see Table 1). As part of the standard intake procedure at the Sinai Centre, patients who score positively on the SCID-5PD screener will be interviewed with the M.I.N.I.-plus and the SCID-5-PD. Patients with potential eligibility based on the in- and exclusion criteria described earlier receive the study information folder from the psychologist who performed the intake with them. If a patient is interested and gives their consent, the intaker informs the researchers to contact the patient. One of the researchers will explain the study to the possible participant and provide the information folders. After a consideration period of at least one week, they will be asked whether they want to take part in the research.

At To/Day 1, the study- intaker will explain the study information once more. If informed consent is obtained, in- and exclusion criteria will again be checked to assess the patient's potential eligibility for participation (Dutch language, , LEC-5/PCL-5, SCID-5-PD screener) and if the patient is included, the CAPS-5 will be performed.

After the interview, the patients receive an online code to fill in additional questionnaires online at the center or at home, if the patient has access to the internet (see Table 1). Total duration of the measurements of To/Day 1 will be ca. two hours (see Table 3).

At To/Day 2, patients are invited for the physical examination (weight and height to calculate Body Mass Index (BMI), blood pressure, hair sample by a research assistant and fasting blood sample as well as questions on cigarette smoking, alcohol and coffee consumption, medication and drug use) and they will be asked to perform a working memory task (N-back-task) outside the scanner and to fill in the last set of questionnaires (see Table 1) either at the Sinai Center or online at home. Total duration of the measurements of To/Day 2 will be ca. 40 minutes (see Table 3).

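### The hormonal/epigenetic predictor and mediator analyses in section 7.1 do not use the medication data the trial collects, so a marker of drug response can be reported as a marker of psychotherapy response

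*Combined protocol and SAP*

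**What the plan says.** **Evidence cited for the markers.** The introduction (section 1, Part B) links the LL 5-HTTLPR genotype to better response of PTSD to drug treatment. On BDNF it states "Lower brain derived neurotrophic factor (BDNF) levels predicted a greater response to pharmacotherapy in PTSD". It then adds: "It is not clear yet if these factors might predict psychotherapy outcome as well".

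**Medication in the trial.** Section 3, under co-intervention, states "Patients may continue taking medication for PTSD throughout the study". Two limits apply: "Patients who started with new medication for PTSD within 1 month prior to the initial screening will be excluded from participation", and "No other psychological or new pharmacological therapy is allowed during treatment". Medication for an acute crisis is permitted and does not lead to exclusion. The MRI subgroup has a stricter rule in section 4.3: an SSRI at a dose stable for three months or more, or low-dose benzodiazepines.

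**Medication data.** At T0/Day 2 (section 5.3) the visit that takes blood and hair also includes "questions on cigarette smoking, alcohol and coffee consumption, medication and drug use". Section 3 says medication use is monitored during the study.

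**Analysis.** Section 7.1 plans mediation analyses: "Secondary analyses will examine whether hormonal and epigenetic factors (5-HTTLPR, BDNF, cortisol/FKBP5-methylation, oxytocin/OXTR) mediate the treatment effects". They use marker levels at T0 and T2, and no covariates are named. The hormonal/epigenetic factors also stand in the candidate list for the machine-learning models. Objective B2 and question 3 under Part B of section 5.3 ask whether they predict treatment outcome. Nowhere in section 7 does medication appear as covariate, predictor, effect modifier, stratifier or sensitivity analysis.

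**The concern.** The trial treats with psychotherapy, but an unknown share of patients will be on PTSD drugs at the same time. For two of the markers, the protocol's own specific evidence is that they track response to such drugs. Suppose one of them is related to outcome only in medicated patients. An analysis that pools medicated and unmedicated patients and does not use medication will still find the marker associated with outcome, and the write-up would attribute this to EMDR, ImRs or the integrated treatments.

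That is the question the introduction leaves open and objective B2 is meant to answer. Objective B aims to improve treatment indication, so a wrongly attributed marker could enter the tool meant to guide the choice between psychotherapies.

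**Working it through.** The plan states no figure on this point, so there is nothing to reproduce. The text check above establishes the gap. The calculations below show only how it operates and which remedy works.

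**Prediction**

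From the documents: N = 252 (section 4.4).

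Assumed:
- marker carriers p = 30%, independent of drug use;
- marker effect d = 0.5 SD in medicated patients and zero in unmedicated patients;
- residual SD 1;
- medicated share m = 20%, 40% or 60%;
- one two-sided test at 5%.

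Pooled marker effect = m × d.

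SE = 1/√(N × p × (1 − p)) = 1/√(252 × 0.30 × 0.70) = 0.137.

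Probability of flagging the marker = 1 − Φ(1.96 − md/SE) + Φ(−1.96 − md/SE).

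For m = 40%: md = 0.20 and md/SE = 1.455, so the probability is 1 − Φ(0.505) plus a negligible lower tail = 31%.

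The closed form was checked by simulation with 3,000 runs per setting, in three models:

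| Medicated | m × d | Closed form | Simulated, medication ignored | Simulated, medication main effect added | Simulated, main effect and marker-by-medication term (marker effect in unmedicated) |
|---|---|---|---|---|---|
| 20% | 0.10 | 11% | 11% | 11% | 5% |
| 40% | 0.20 | 31% | 30% | 30% | 5% |
| 60% | 0.30 | 59% | 56% | 56% | 5% |

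The main effect changes nothing, because the marker coefficient still averages the medicated and unmedicated effects. Only the interaction separates them.

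Sensitivity:
- Over m = 20% to 80% and d = 0.3 to 0.8 SD, the closed form runs from 7% to over 99%.
- With fewer patients the rate falls. At m = 40% and d = 0.5, N = 189 (252 × 0.75, the plan's dropout rate) gives SE = 0.159, md/SE = 1.26 and 24%. N = 80 gives SE = 0.244, md/SE = 0.82 and 13%.

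**Mediation**

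Randomisation protects the treatment-to-mediator path from baseline medication. The mediator-to-outcome path has no such protection. Assume medication shifts the marker change by g SD and the outcome by t SD, and that the marker has no effect of its own. The spurious slope is then

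g × t × m(1 − m) / (1 + g² × m(1 − m)).

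At m = 40%:
- g = t = 0.3: 0.09 × 0.24 / (1 + 0.09 × 0.24) = 0.021
- g = t = 0.5: 0.25 × 0.24 / (1 + 0.25 × 0.24) = 0.057

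Over m = 20% to 60% the range is 0.014 to 0.057 outcome SD per unit of marker. This is small, and adjusting for T0 medication removes it in this model. The values of g and t are assumptions.

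**Cost of the interaction model**

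The 95% half-width for the marker effect is 1.96 × 0.137 = 0.27 SD in all 252 patients. In the unmedicated at m = 40% (252 × 0.60 = 151 patients) it is 1.96 × 1/√(151.2 × 0.21) = 0.35 SD. At m = 60% it is 0.43 SD.

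**The case against.** **The plan does not run the test used in the illustration.** Section 7.1 classifies responders with methods such as random forest and reports sensitivity, specificity and likelihood ratios. No marker is declared by a p-value. This stands: the percentages are not error rates of this plan. But a forest without medication as an input cannot make the distinction either, and would credit the marker.

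**Prediction is not causation.** A marker that predicts in a population allowed to take drugs does predict there. This also stands, and it limits the point to attribution. Attribution matters because the introduction poses the psychotherapy question as open and objective B is about choosing treatment.

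**The design already limits the problem.** The one-month rule and the ban on new drugs mean that part of the drug response may already be in the baseline score. The MRI subgroup has tighter limits, and the numbered machine-learning questions name only brain activity. All of this reduces the exposure. It does not remove it for the blood and hair markers, which are in the candidate list and in the mediation analyses.

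**Covariates could be added.** The covariate list described as a minimum belongs to the primary CAPS-5 mixed model. Nothing commits the mediation or prediction analyses to medication, and a main effect alone would not be enough.

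**Stronger readings that the documents do not support.** A reader might infer that:
- the comparison between arms is confounded by medication, but randomisation balances baseline medication in expectation;
- drug response is the only evidence offered for these markers, but the Summary links all four hormonal/epigenetic groups to PTSD treatment outcome in general;
- smoking, coffee or BMI must also be adjusted for, but no section says that they alter these markers.

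**Conclusion.** The point holds as a gap in attribution. Following section 7.1 as written, a marker of drug response can be reported as a predictor or mediator of psychotherapy outcome. The case is strongest for 5-HTTLPR and BDNF, where the protocol itself cites pharmacotherapy evidence. It is stronger for prediction, which compares across patients, than for mediation, where only the mediator-to-outcome path is exposed and the illustrated bias is small.

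A reader might take the 11% to 56% as an estimate for this trial. It is not. The medicated share, the carrier share, the effect size and full uptake of blood sampling are all assumptions, and section 5.3 and Table 3 leave open that blood and hair come from only part of the sample. What does not depend on those values is that a medication main effect fails to separate the two explanations, whereas a marker-by-medication term does so in this model.

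The primary treatment comparison is unaffected. This is an inexpensive improvement to the Part B and mediation analyses, and worth making.

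**What to change.** In section 7.1:

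1. Add PTSD medication at T0 (yes/no and class) to the candidate predictors for the machine-learning models.
2. For the hormonal/epigenetic markers, above all 5-HTTLPR and BDNF, report a supportive regression with a marker-by-medication term, and give the marker effect in patients not on PTSD medication.
3. In the mediation analyses, adjust the mediator-to-outcome path for T0 medication.
4. Describe by arm any medication started or changed between T0 and T2. Do not exclude these patients: the change happens after randomisation and may differ by arm, so exclusion could itself introduce bias.

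Baseline medication is already asked and later use is already monitored, so no visit, eligibility rule or treatment changes. The cost is precision. Under the illustrative inputs, the half-width for the marker effect widens from 0.27 SD in all patients to 0.35 SD in the unmedicated at 40% medicated and 0.43 SD at 60%, and it would be wider with fewer blood samples. The result in unmedicated patients should therefore be labelled supportive, and a null finding there should not be read as evidence of no effect.
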